**10. Describe the means of analyzing the data and evaluating the results.**

- *State the anticipated methods to be used for analysis and interpretation of the data.*
- *The methods must compliment the design of the study and the nature of the data which is being collected.*

This study investigates horizontal binocular conjugacy and ocular motor fatigue in MS patients with INO and the effects of treatment (dalfampridine) while eye movements are recorded during a 10-minute saccadic fatigue test. Patients will undergo clinical eye movement examination, visual performance assessment including reading acuity and speed, gait assessment, assessment of symptomatic fatigue, disability arising from visual dysfunction as well as quality of life, using available self-administered questionnaires and scales, and eye movement recording, before and after treatment. The treatment portion of the study will be conducted following a randomized, placebo-controlled, double-blind, crossover trial design, which will include a period of wash out of at least two weeks between treatment with dalfampridine and placebo. A minimum of 2 weeks is necessary to ensure wash out, however a washout period longer than 2 weeks will not confound the study results. There will be a total of 4 evaluations: at baseline, after washout, and after treatment with both dalfampridine and placebo. Subject participation will last an estimated 10-14 weeks. We anticipate most subjects will participate for 10 weeks, however due to unforeseen circumstances a subject may be unable to keep a scheduled appointment lengthening the overall time of their participation. In order to test our hypotheses, we use the following outcome measures, at time of each evaluation. A. Eye movement assessment: changes in binocular horizontal conjugacy at baseline and following the saccadic fatigue test using 1) abducting/adducting eye ratio for saccadic peak velocity (pulse size ratio); 2) time difference in occurrence of peak acceleration in the adducting vs. the abducting eye (pulse time delay). These measures of conjugacy of horizontal saccades are applied to data collected continuously throughout the fatigue test. B. Symptomatic fatigue assessment using 1) Fatigue Severity Scale (FSS); 2) Modified Fatigue Impact Scale (MFIS); C. Visual function assessment using 1) MNREAD acuity charts for reading acuity and speed; 2) King-Devick test for saccades performance; D. Gait assessment using 1) 25-foot Walk Test; 2) 6-minute Walk Test. E. Visual disability and quality of life assessment using 1) NEI-VFQ-25 and NOS; 2) MS Quality of Life Inventory. Standard statistical measures, such as paired dependent t-test, will be employed to determine significance of our results.

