**13. Please describe the research design and all study related procedures.**

- *Describe **ALL PROCEDURES ASSOCIATED WITH THIS RESEARCH**. This includes standard of care and research procedures.*
- *For complex studies please include diagrams and tables. Be sure to describe when each procedure will be performed. Be sure to provide information for **each cohort, including normal controls**).*

Patients cohorts (n=30).

Enrollment. [name] will be responsible for enrolling all patients for the study, whether he is the primary neurologist caring for the patients or whether they are being referred to him for possible enrollment in the study.

All patients will undergo neurological evaluation (medical history, clinical neurological examination, including eye movements exam, and blood work for renal function panel) prior to selection to establish whether or not they meet the study inclusion criteria. Possible female participants will also undergo a urine pregnancy test. [name] will evaluate all patients as above.

Randomization and masking. Patients will be randomized to study drug or placebo for the first 4 weeks of treatment then, after a wash-out period of at least 2 weeks, they will cross-over to placebo and study drug respectively for another 4 weeks of treatment. Randomization process will be carried out by a VA research pharmacist. The patient, the PI, and all personnel and investigators involved in the study will be masked to treatment assignment. To avoid the possibility of a patient running out of the study drug/placebo at the time of the

2nd or 4th visit, for example in case of visit cancellation due to unforeseeable circumstances, the study drug/placebo will be sent out for 5 weeks. However, every effort will be made to schedule patients as close as possible to the 4-week mark for the 2nd and 4th visit. Additionally, all unused study medications will be returned by the subject to the laboratory at the 2nd and 4th visits.

Procedures to be performed at Evaluation 1 ,2 ,3 ,4.

Video tape of subjects' eye movements.

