**Eye Movement Recording.** Eye movements will be recorded using the EyeLink II system, (SR Research Ltd.). Subjects will sit in a 110-ft-lb vestibular chair (CNC Engineering), with head restrained, during all the experimental paradigms, and will follow a visual stimulus (a red laser spot) projected onto tangent screen. The EyeLink signal from each eye will be calibrated. We will obtain a baseline monocular and binocular viewing recording of eye movements then will perform the 10-minute saccadic fatigue test as previously described [Matta et al, 2009]. Patients will make horizontal saccades in response to 20-degree jumps, at 0.5 Hz across the midline (i.e., 1 saccade per second), of the visual target (laser spot).

At evaluations 2 and 4, patients will hold the am dose (dalfampridine or placebo), will undergo baseline eye movement recording, then will be recorded again 3 hours after taking their dose in the same session.

Visual function assessment using MNREAD acuity charts for reading acuity and speed and the King-Devick test for saccades performance. [name] will carry out these assessments.

Symptomatic fatigue assessment using self-administered questionnaires: the Fatigue Severity Scale (FSS) and the Modified Fatigue Impact Scale (MFIS).

Gait assessment using the 25-foot Walk Test and the 6-minute Walk Test. [name] will carry out these assessments.

Visual disability and quality of life assessment using the following self-administered scales: NEI-VFQ-25 and NOS; and the MS Quality of Life Inventory.

Renal function panel (serum) at baseline, to be repeated after 4 weeks and at the end of the trial. Phlebotomy will be performed by a lab technician in the blood work laboratory located in the first floor of the LSDVAMC.

Normal controls cohort (n=20).

**Enrollment.** [name] will be responsible for enrolling all age-matched normal controls for the study, including possibly residents, house staff and employees of the LSDVAMC and Case.

All controls will undergo clinical evaluation of vision and eye movements to confirm they have normal visual and ocular motor functions.

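### Item 10 gives no role to the off-treatment period baselines (Evaluations 1 and 3); adjusting the drug-minus-placebo difference for them is a cheap improvement

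*Combined protocol and SAP*

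**What the plan says.** Section 3, item 10 describes the treatment part as a "randomized, placebo-controlled, double-blind, crossover trial design" and sets the visits: "There will be a total of 4 evaluations: at baseline, after washout, and after treatment with both dalfampridine and placebo". It adds that "we use the following outcome measures, at time of each evaluation", so the whole outcome battery is repeated each time. Item 13 fixes the order: "every effort will be made to schedule patients as close as possible to the 4-week mark for the 2nd and 4th visit". Evaluations 2 and 4 therefore close the two treatment periods, and Evaluations 1 and 3 precede them, off treatment.

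The analysis plan is one sentence: "Standard statistical measures, such as paired dependent t-test, will be employed to determine significance of our results". It does not say which of the four values form the pair, and it names no covariate.

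For eye movements, item 13 adds a second recording within two of the visits: "At evaluations 2 and 4, patients will hold the am dose (dalfampridine or placebo), will undergo baseline eye movement recording", and they are recorded again 3 hours after the dose. The first of these is called a baseline, although it is made after about four weeks on drug or placebo.

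**The concern.** Four values per patient and outcome allow at least four analyses under the paired t-test label or close to it:

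- **Unadjusted:** drug against placebo at Evaluations 2 and 4.
- **Change score:** drug-period change minus placebo-period change.
- **Adjusted:** the Evaluation 2 and 4 difference, regressed on the period-baseline difference.
- **Within drug:** after against before on drug alone. This is not placebo-controlled.

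The first three estimate the same effect with different precision, and item 10 does not choose between them. Unless the choice is made in advance, the contrast could be picked after the data are seen, and precision available from data already collected may be lost. The within-drug comparison is open to practice effects on repeated performance tests. For the eye measures it is also open to the effect of a second recording some hours into the visit.

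**Working it through.** **The plan's own figure.** Item 11 gives 27 patients for an effect size of 0.5, alpha 0.05 and power 0.85, without stating sidedness or which SD scales the effect. The paired normal formula n = ((z_alpha + z_power)/d)² gives 28.76 one-sided (29 patients) and 35.91 two-sided (36). The exact t calculation gives 31 and 38. The one-sided normal result is the closest to 27. Planned enrolment is 30.

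**Inputs for the comparison.** n = 30 and d = 0.5 come from item 11. Taking d in SD units of the paired drug-minus-placebo difference, and testing two-sided at 5%, are assumptions.

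**Notation.** For one patient, D is drug minus placebo at Evaluations 2 and 4. B is the matching baseline difference: drug-period baseline minus placebo-period baseline, from Evaluations 1 and 3. Assume D and B have the same SD, σ, and correlation r.

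**Variances.**
- Unadjusted: Var(D) = σ².
- Change score: Var(D − B) = 2σ²(1−r), a ratio of 2(1−r).
- Adjusted with estimated slope: σ²(1−r²), a ratio of 1−r². Estimating the slope multiplies this by about 1 + 1/(n−4) = 1 + 1/26 = 1.038.
- Gap between the last two ratios: 2(1−r) − (1−r²) = (1−r)², which is never negative. Apart from the cost of estimating the slope, adjustment is never less precise than change scores.

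**Power** (noncentral t; noncentrality 0.5√30 = 2.739 divided by the square root of the variance ratio):

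| r | Change ratio 2(1−r) | Adjusted ratio 1−r² | Unadjusted | Change score | Adjusted |
|---|---|---|---|---|---|
| 0 | 2.0 | 1.00 | 0.754 | 0.465 | 0.737 |
| 0.3 | 1.4 | 0.91 | 0.754 | 0.609 | 0.776 |
| 0.5 | 1.0 | 0.75 | 0.754 | 0.754 | 0.850 |
| 0.7 | 0.6 | 0.51 | 0.754 | 0.927 | 0.953 |

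Adding a period term moves these by about 0.001. Simulation with a period term agreed: at r = 0 the change-score variance ratio was 2.01, and power was 0.755, 0.468 and 0.739.

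**Break-even.** Adjustment matches the unadjusted test when (1−r²) × 27/26 = 1, so r² = 1/27 and r = 0.19. Below about 0.2 it costs up to 0.754 − 0.737 = 0.017 in power; above that it gains.

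**What r depends on.** With equal variances, within-period correlation w and between-period correlation b, r = (w − b)/(1 − b). If all four visits are equally correlated, r = 0. With b = 0.6, w = 0.7 gives r = 0.25 and w = 0.8 gives r = 0.5. These are illustrations, not trial data.

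**Residual drug effect at Evaluation 3.** Suppose r = 0.5, and that drug-first patients (half the sample) keep an effect of 0.3 SD at Evaluation 3 that has gone by Evaluation 4. The mean of B becomes −0.15. The slope becomes about 0.5/(1 + 0.15²) = 0.489. The adjusted estimate is then 0.50 + 0.489 × 0.15 = 0.57, while the unadjusted estimate stays at 0.50.

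**The case against.** A reader might infer that the plan has chosen a wrong analysis, testing drug against its own baseline, because item 10 refers to "eye movement recording, before and after treatment". The documents do not support that. The phrase ends a list of assessments and says when they are made, not how they are compared. The t-test is offered only as an example, and in a placebo-controlled crossover the natural contrast is drug against placebo. The t-test may also be meant for the fatigue aim, where the change across the 10-minute test is itself an outcome and supplies two of the three power figures in item 11.

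A reader might also infer that change scores double the variance as a rule. That is the r = 0 case. Above r = 0.5 they beat the unadjusted test.

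Three further objections stand in part:

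- The gain from adjustment is not assured. If r is near 0, the plain Evaluation 2 against 4 comparison is the best of the three by a small margin.
- Evaluation 3 follows the first treatment, so adjustment brings in any drug effect that outlasts the washout. Item 10 asserts that two weeks is enough, so this may be small, but it is a real cost.
- The effect of a second recording on the same day occurs in both periods. If similar under drug and placebo, it cancels from any drug-minus-placebo contrast and threatens only within-drug tests.

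**Conclusion.** The point holds as a gap in specification with a cheap improvement available, not as an error in the plan. Item 10 leaves the treatment contrast and the use of Evaluations 1 and 3 unstated. The unadjusted contrast would be valid. Change scores are a gamble on an unknown r: power runs from 0.47 at r = 0 to 0.93 at r = 0.7. Adjustment removes most of that gamble, with power from 0.74 to 0.95 over the same range, against 0.75 unadjusted throughout.

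These figures assume 30 completers, equal variances at all visits, a true difference of 0.5 SD of the paired difference, a two-sided 5% test and no residual drug effect at Evaluation 3. The documents give no value for r, so they do not show how much precision would be gained.

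**What to change.** Amend item 10 to state that:

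1. The treatment effect for each outcome is the within-patient drug-minus-placebo difference at Evaluations 2 and 4. It is adjusted by regression for that patient's period-baseline difference (Evaluation 1 or 3, whichever preceded each treatment), with the coefficient estimated and not fixed at 1.
2. For the eye measures, the outcome recording at Evaluations 2 and 4 (pre-dose or 3 hours post-dose) is named in advance, and the on-treatment pre-dose recording is not the period baseline.
3. Before-after tests within one treatment are descriptive and are not evidence of a drug effect.
4. The unadjusted Evaluation 2 against 4 contrast is reported as a sensitivity analysis, because the adjusted estimate would be affected by any drug effect still present at Evaluation 3.

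The cost is a few sentences and one covariate, with no new visits or data. The statistical price is one degree of freedom, about 1 to 2 percentage points of power when r is near 0 and nothing once r reaches about 0.2, plus the Evaluation 3 sensitivity covered by point 4.

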With this proposal we expect to learn about mechanisms of motor fatigue in MS and provide a neurophysiological model for it, using a known eye movement abnormality often found in MS. More in general, we aim at studying the impact certain eye movement disorders have on often under-recognized visual dysfunction in patients affected. We will also evaluate the effect of a pharmacological treatment for a certain eye movement disorder in MS patients. Evidence suggests that primary motor fatigue, a highly disabling symptom in MS patients, originates within the CNS but a neurophysiological model to explain its underlying mechanisms is still lacking. As a consequence, medical treatment for fatigue are generally unsatisfactory. Moreover, fatigue remains difficult to objectify in the clinical settings as its assessment solely relies on subjective reports through standard questionnaires filled by patients (symptomatic fatigue). With this project, we propose a characteristic eye movement abnormality of eye coordination, internuclear ophthalmoparesis (INO), as a simple and accessible model for primary motor fatigue in MS. INO results from demyelination of a specific white matter tract in the brainstem (the medial longitudinal fasciculus, MLF) and is clinical evident with slowing of the adducting eye (i.e., the eye moving towards the nose) during horizontal gaze shifts, while the abducting eye (i.e., the eye moving away from the nose) is normal. Preliminary results in a small MS group show that patients with INO exhibit changes in ocular conjugacy (i.e., they show ocular motor fatigue) during a 10-minute recording of their fast eye movements (saccadic fatigue test), but normal subjects do not. In this respect, our hypotheses are: 1) ocular motor fatigue can complicate INO and is associated with worse scores of symptomatic fatigue than INO without ocular motor fatigue; 2) ocular motor fatigue is due to deterioration of neural conduction of the signal

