needed to generate a saccade along the demyelinated MLF, which might be representative of a major component of primary motor fatigue in MS. The second part of the project concerns testing the effects of dalfampridine (a potassium channel blocker that enhances neural conduction along demyelinated axons) on MS-related INO with or without associated ocular motor fatigue. Visual dysfunction in MS patients with INO is a major cause of disability but no medical therapy is available. Our preliminary results document improved binocular conjugacy in three MS patients taking dalfampridine. In this respect, our hypotheses are: 1) dalfampridine improves visual performance in MS patients with INO and counteracts ocular motor fatigue; 2) improvement of INO and ocular motor fatigue with dalfampridine diminishes visual disability and improves quality of life in MS.

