
**11. Provide a BRIEF DESCRIPTION of how the estimated number of study subjects needed for this research was determined**

- *If this is a quantitative study provide the method of determining sample size estimates.*
- *If multiple studies are planned provide a power analysis or justification for each one.*

To determine the number of subjects needed for this study, we conducted a power analysis based on our preliminary data of increase in pulse size ratio and pulse time delay after the 10-minute fatigue test in two different sample populations of MS patients with INO. Based on a large effect size of 0.93, we found that we will need a sample size of 9 patients to reach a power of 0.80 (alpha 0.05) for the first outcome measure (pulse size ratio). Based on a moderately large effect size of 0.63, we found that we will need a sample size of 17 patients to reach a power of 0.80 (alpha 0.05) for the second outcome measure (pulse time delay). Because only one out of three patients showed clinically significant changes of pulse size ratio and pulse time delay after dalfampridine, while changes were subclinical in the other two patients, we were not able to provide a power analysis for the expected effects of dalfampridine in our trial. However, we found that for a clinically meaningful effect size of 0.5, with alpha of 0.05, we will need a sample size of 27 patients to yield a power of 0.85 [Norman et al., 2000]. Thus we aim at recruiting, studying and treating 30 patients.

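### No primary outcome, testing order or multiplicity rule is set for the drug-versus-placebo comparison, so its false-positive rate is not fixed

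*Combined protocol and SAP*

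**What the plan says.** **Outcomes and test (item 10).** After "In order to test our hypotheses, we use the following outcome measures, at time of each evaluation" come five lettered domains: A eye movements, B symptomatic fatigue, C visual function, D gait, E visual disability and quality of life. They hold ten numbered measures, or twelve scores if MNREAD acuity and speed, and NEI-VFQ-25 and NOS, are counted separately. Domain A concerns "changes in binocular horizontal conjugacy at baseline and following the saccadic fatigue test", measured by pulse size ratio and pulse time delay. The only decision statement is "Standard statistical measures, such as paired dependent t-test, will be employed to determine significance of our results".

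**Drug hypotheses (item 9).** The first is that "dalfampridine improves visual performance in MS patients with INO and counteracts ocular motor fatigue". The second is that "improvement of INO and ocular motor fatigue with dalfampridine diminishes visual disability and improves quality of life in MS". Symptomatic fatigue appears in a separate, non-drug hypothesis, that ocular motor fatigue "is associated with worse scores of symptomatic fatigue than INO without ocular motor fatigue". Gait appears in none of the hypotheses.

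**Sample size (item 11).** Pulse size ratio and pulse time delay are labelled the first and second outcome measure where the plan sizes their increase after the 10-minute fatigue test. For the drug, the plan says it could not give a power analysis, because "only one out of three patients showed clinically significant changes of pulse size ratio and pulse time delay after dalfampridine". It then states that "for a clinically meaningful effect size of 0.5, with alpha of 0.05, we will need a sample size of 27 patients", with power 0.85, and plans 30 patients. No outcome is attached to the 0.5, and sidedness is not given.

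**Recordings (item 13).** Evaluations 2 and 4 each have one eye movement recording before the held morning dose and another three hours after it. Neither is assigned to the drug-placebo comparison.

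**The concern.** A crossover trial that tests its hypotheses for significance needs to say in advance which drug-minus-placebo difference carries the claim. Here three choices are open: the measure within each domain, how the two parts of the first drug hypothesis combine, and the recording used at evaluations 2 and 4. Item 10 also does not fix whether conjugacy enters as the level following the fatigue test or as the increase over it.

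If these choices are made once results are known, a nominal 0.05 no longer describes the chance of a false claim of benefit. The stated power has the same gap, since it belongs to no particular outcome.

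**Working it through.** **1. The plan's own figure.** Inputs from item 11: d = 0.5, alpha 0.05, power 0.85, N = 27, with 30 planned. The paired normal approximation is n = ((z_alpha + z_power)/d)².
- One-sided: ((1.645 + 1.036)/0.5)² = 28.8, so 29, within two patients of the stated 27.
- Two-sided: ((1.960 + 1.036)/0.5)² = 35.9, so 36.

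Exact paired-t power uses a noncentral t with noncentrality d√N:

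| N | d√N | One-sided (critical t) | Two-sided (critical t) |
|---|---|---|---|
| 27 | 2.598 | 0.81 (1.706) | 0.71 (2.056) |
| 30 | 2.739 | 0.85 (1.699) | 0.75 (2.045) |

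So 0.85 is reached at N = 30 one-sided, and not at N = 27 under either choice.

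**2. Which scores bear on the drug hypotheses.** Domain A (2 scores) matches INO and ocular motor fatigue. Domain C (3: MNREAD acuity, MNREAD speed, King-Devick) matches visual performance. Domain E (3: NEI-VFQ-25, NOS, MS Quality of Life Inventory) matches visual disability and quality of life. Total 2 + 3 + 3 = 8. The four fatigue-scale and gait scores are left out.

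**3. False-benefit rate if any one significant score counts.** Assumptions: no true effect; equal correlation ρ between test statistics (the documents give none). With c the critical value (1.960 two-sided, 1.645 one-sided), φ and Φ the standard normal density and distribution function, and k scores:

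rate = 1 − ∫ φ(u) · Φ((c − √ρ·u)/√(1 − ρ))^k du

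At ρ = 0 this is 1 − 0.975^k (two-sided tests, benefit direction only) or 1 − 0.95^k (one-sided). For k = 8: 1 − 0.975^8 = 0.183 and 1 − 0.95^8 = 0.337.

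| Scores | Test at 0.05 | ρ = 0.7 | ρ = 0.5 | ρ = 0 |
|---|---|---|---|---|
| 1 | two-sided | 2.5% | 2.5% | 2.5% |
| 2 conjugacy | two-sided | 4.2% | 4.5% | 4.9% |
| 8 hypothesis-linked | two-sided | 9.5% | 12.5% | 18% |
| 1 | one-sided | 5% | 5% | 5% |
| 2 conjugacy | one-sided | 8.0% | 8.8% | 9.75% |
| 8 hypothesis-linked | one-sided | 17% | 22% | 34% |

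**4. Joint rule for the first drug hypothesis.** Suppose success needs a benefit on at least one of 3 visual scores and at least one of m conjugacy tests. With p(u) = Φ((c − √ρ·u)/√(1 − ρ)):

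rate = ∫ φ(u) · (1 − p(u)³) · (1 − p(u)^m) du

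With two-sided 0.05 tests and m = 2, the rate is 1.7% (ρ = 0.5) to 2.2% (ρ = 0.7). If two versions of each conjugacy measure stay open, such as level and increase, m = 4 and the rate is 2.6% to 3.1%, against 2.5% for one test.

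**The case against.** The best counter-evidence is item 11's ordinal labels, which could be read as making pulse size ratio primary. They belong to the sizing of the within-test increase. The statement that the drug effect could not be powered comes just after them, and they give no rule for combining the two measures. They show a leaning towards conjugacy, as does item 14's description of the trial, but no designation.

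Several stronger readings are tempting and do not stand:

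- *That the plan does not connect scores to hypotheses.* The domain headings do so broadly. What is missing is the choice within a domain and the combination rule.
- *That ocular motor fatigue is undefined.* Item 9 describes it as a change in conjugacy during the 10-minute recording, and item 11 sizes on an increase. Both point to the increase over the test; item 10 simply does not fix it.
- *That all twelve scores compete for the drug claim.* Four of them serve no stated drug hypothesis, so a twelve-score error rate overstates the problem.
- *That any single significant score would be claimed as success.* The plan does not say this. The first drug hypothesis joins its parts with an "and"-type conjunction, and a strict joint reading with two conjugacy tests keeps the rate below 2.5%. That protection is lost if two versions of each conjugacy measure remain available.
- *That testing is one-sided.* The stated sample sizes fit one-sided tests better, but the plan does not say so; hence both cases are shown.

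The masking in item 13 protects the measurements; it does not stop a rule being chosen after the results are seen. Some front pages and the flow diagram were not in the text available, so the finding is limited to what could be read. Items 10 and 11, where this content belongs, were available.

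**Conclusion.** The omission is real and should be corrected. The available text leaves the primary contrast, the testing order and the multiplicity rule for drug versus placebo unstated. Depending on the rule later adopted, two-sided 0.05 testing gives a false-benefit rate from about 2% (joint rule, two conjugacy tests) to 10-13% (any of eight scores), against 2.5% for one test. One-sided testing puts the any-of-eight rate at 17-22%, against 5%. These ranges rest on no true effect and an assumed equal correlation of 0.7 to 0.5; at zero correlation the any-of-eight rates are 18% and 34%. They show what an unstated rule permits and do not predict how the investigators would report. Separately, the stated power of 0.85 at 27 patients is not reproduced by a paired t-test at either sidedness.

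**What to change.** **Item 10, before unblinding.** Name one primary drug-minus-placebo contrast, for example the increase in pulse size ratio over the fatigue test. State which recording at evaluations 2 and 4 it uses (pre-dose or three hours post-dose). Test pulse time delay, defined the same way, second and only if the primary is significant, each at 0.05. Report all other outcomes as secondary estimates with confidence intervals.

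**Item 11.** Tie the effect size of 0.5 to that primary, state the sidedness, and replace the power statement with the paired-t values in the working for N = 27 and N = 30.

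**Cost.** One paragraph and one sentence, submitted as an IRB modification as the Version Date note requires, with no change to visits or sample size. The visual-performance part of the first drug hypothesis and all of the second become supportive only. The claim rests on a physiological measure. Pulse time delay cannot be claimed if the primary fails. The stated power becomes less favourable. A Bonferroni split would cost more: at d = 0.5 and N = 30, two-sided power per outcome falls to 0.65 for two outcomes (each at 0.05/2) and 0.43 for eight (each at 0.05/8).

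### The crossover analysis names only a paired t-test, as an example; a period-adjusted analysis with balanced sequences would be a cheap, conditional improvement

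*Combined protocol and SAP*

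**What the plan says.** All references are to Section 3 of the combined protocol and SAP.

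- **Design (item 10):** a "randomized, placebo-controlled, double-blind, crossover trial design, which will include a period of wash out of at least two weeks". Item 13 adds that patients start on drug or placebo for 4 weeks and, after washout, "they will cross-over to placebo and study drug respectively for another 4 weeks of treatment".
- **Analysis (item 10):** the whole statement is "Standard statistical measures, such as paired dependent t-test, will be employed to determine significance of our results". No other test or model is named anywhere in the readable text. The form's own instruction for this item is "The methods must compliment the design of the study and the nature of the data which is being collected".
- **Evaluations (items 10 and 13):** there are four: baseline, after the first treatment, after washout, and after the second treatment. The eye-movement, fatigue, visual function, gait and quality-of-life measures are taken at each.
- **Eye movements:** item 10 defines the outcome as "changes in binocular horizontal conjugacy at baseline and following the saccadic fatigue test". Item 13 says that at Evaluations 2 and 4 patients hold the morning dose, "will undergo baseline eye movement recording, then will be recorded again 3 hours after taking their dose in the same session". It does not say which of the two recordings enters the drug–placebo comparison.
- **Allocation (item 13):** "Randomization process will be carried out by a VA research pharmacist". No ratio, blocking or number per sequence follows in the text. The flow diagram is not shown in the copy reviewed and could give numbers per sequence.
- **Size (item 11):** "for a clinically meaningful effect size of 0.5, with alpha of 0.05, we will need a sample size of 27 patients" for power 0.85, and 30 are to be recruited.

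**The concern.** In a two-period crossover each patient's drug-minus-placebo difference contains the period effect, with opposite sign in the two sequences. A paired t-test that ignores sequence treats that systematic split as noise. If the sequences are equal in size, the period effect cancels from the mean but inflates the SD, so power falls. If they are unequal, part of the period effect also stays in that trial's estimate.

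A period effect is plausible, because several outcomes are repeated performance tests or self-reports over 10–14 weeks. How far it reaches the analysis depends on a contrast that the plan does not name:

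- Post-treatment values alone (Evaluation 2 against 4) are exposed to any period effect.
- Changes from each period's own baseline (Evaluation 2 minus 1 against 4 minus 3) cancel a stable level shift, for every outcome. Only a period effect on the change remains, such as unequal practice gains.
- A within-session eye-movement contrast (fatigue-test change, or pre-dose against 3 hours post-dose) likewise cancels a stable shift.

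**Working it through.** **Inputs from item 11:** N = 30, effect 0.5, alpha 0.05. Sidedness is not stated, so both are shown.

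**Assumptions:** the 0.5 is in SDs of the paired difference. The period effect π (period 2 minus period 1, in SDs of the analysed contrast) is 0, 0.1, 0.25 or 0.5. The splits are 15/15 and 13/17.

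**The plan's own figure.** A one-sided paired t-test comes close to item 11's fatigue-test figures: N = 9 for effect 0.93, and N = 18 for effect 0.63 (17 stated; power at 17 is 0.7997). It does not give 27 for the drug effect: power at 27 is 0.812 one-sided and 0.706 two-sided, not 0.85. At the planned 30 it is 0.848 one-sided and 0.754 two-sided. That mismatch is a separate matter; the work below starts from N = 30.

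**Model.** With SD 1, the drug-minus-placebo difference has mean τ − π in the n1 drug-first patients and τ + π in the n2 placebo-first patients.

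- *Plain paired t-test:* the expected estimate is τ + π(n2 − n1)/N. The sum of squares is noncentral chi-square with 29 df and noncentrality 4·n1·n2·π²/N. Power follows by numerical integration.
- *Period-adjusted:* the average of the two sequence means, with SE √[(1/n1 + 1/n2)/4] and 28 df. Power is from the noncentral t and does not depend on π.

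**Equal sequences, 15/15.** The estimate stays at 0.50. At π = 0.5 the noncentrality is 4·15·15·0.25/30 = 7.5, so the expected variance is (29 + 7.5)/29 = 1.26 instead of 1. The adjusted SE is √[(2/15)/4] = 0.183, and 0.5/0.183 = 2.74.

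| π | Plain, two-sided | Adjusted, two-sided | Plain, one-sided | Adjusted, one-sided |
|---|---|---|---|---|
| 0 | 0.754 | 0.753 | 0.848 | 0.848 |
| 0.1 | 0.751 | 0.753 | 0.846 | 0.848 |
| 0.25 | 0.734 | 0.753 | 0.835 | 0.848 |
| 0.5 | 0.672 | 0.753 | 0.795 | 0.848 |

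The two-sided loss is about 2 points at 0.25 SD and 8 at 0.5 SD; one-sided it is about 1 and 5.

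**Unequal sequences, 13/17.** The shift is π × 4/30, with sign set by which sequence is larger.

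- π = 0.25: shift 0.033, so the estimate is 0.47 or 0.53. Plain two-sided power is 0.67 or 0.79, against 0.745 adjusted.
- π = 0.5: shift 0.067, so the estimate is 0.43 or 0.57. Plain two-sided power is 0.54 or 0.79, against 0.745 adjusted.

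**Averaged over simple 1:1 randomisation (an assumption; not stated).** A split of 13/17 or worse has probability 58%. Plain two-sided power averages 0.754, 0.750, 0.728 and 0.658 for the four values of π, against 0.738 adjusted. The two cross at about π = 0.20. Averaged this way the plain test is unbiased and rejects a true null 5% of the time.

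**Within-session contrast, 15/15 (simulation).** A stable level shift of 1 SD in both recordings of period 2 leaves plain power at 0.754 two-sided and 0.848 one-sided, so nothing is lost.

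**The case against.** **No wrong method is stated.** The t-test is given as an example, in a form field asking for anticipated methods, so a period-adjusted analysis is permitted. This stands. A reader might infer that the plan commits to an invalid test; the text does not support that.

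**Period baselines exist for every outcome.** Since all measures are taken at Evaluations 1 and 3 as well, a paired t-test on changes would cancel a stable level shift for questionnaires, reading, King-Devick and gait too, not only for eye movements. This stands and limits the concern. The power losses above apply to those outcomes only if post-treatment values are compared, or if the change itself differs by period.

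**The harm is assumed.** No document gives a period effect, and the largest value used equals the whole target drug effect. At 0.1 SD and 15/15 the loss is negligible. This stands.

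**Imbalance is not systematic bias.** A reader might infer that the drug estimate is biased or the error rate inflated. Over simple randomisation neither is so; the 13/17 shift is chance imbalance in one realised trial. The flow diagram, not shown, may also fix the balance.

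**The 0.5 may be on another scale.** If it is in between-patient SDs, the SD of the difference is √[2(1 − ρ)]. At an assumed ρ = 0.5 this is 1 and the figures are unchanged. At ρ = 0.7, plain two-sided power at 15/15 is 0.93, 0.91 and 0.86 for period effects of 0, 0.25 and 0.5 on that scale. The loss then remains, but from a higher level.

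What survives is that permission is not specification: a better-matched method is available at almost no cost.

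**Conclusion.** The point holds as a minor, conditional improvement. For a two-sequence, two-period crossover the plan names only a paired t-test, as an example, and the readable text gives no period term and no sequence balance. With no period effect in the analysed contrast, nothing material is lost. With one of 0.25 to 0.5 SD at 15/15, the plain test loses about 2 to 8 points of power two-sided, or 1 to 5 one-sided. At 13/17 the same effects move that trial's estimate by 0.03 to 0.07 SD in either direction, against a target of 0.5.

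These sizes rest on assumed period effects, on assumed splits, and on reading 0.5 as SDs of the paired difference. The documents do not show that a period effect exists, nor that the trial's conclusion would be wrong without the change.

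**What to change.** **Item 10.**

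- Analyse the drug–placebo contrast with the two-sequence, period-adjusted analysis of within-patient differences, or the equivalent mixed model with treatment and period fixed and patient random.
- For each outcome, state whether the contrast uses post-treatment values or changes from the Evaluation 1 and 3 baselines.
- For eye movements, state which recording at Evaluations 2 and 4 is used.
- Keep the paired t-test for the within-session fatigue-test comparison.

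**Item 13.** Have the research pharmacist allocate the two sequences in permuted blocks of varying size, unless the flow diagram already fixes the balance.

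**Cost.** Wording only, no new data, and one degree of freedom. If there is no period effect, the two-sided power cost is about 0.1 point at 15/15 (0.7540 to 0.7529) and about 1 point at 13/17 (0.754 to 0.745). Averaged over simple randomisation it is about 1.6 points (0.754 to 0.738) if blocking is not adopted, which is why the two changes belong together.
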